### **3. Background and significance:**

Over the last 20 years, opioid use disorder and related deaths have risen to epidemic proportions in the United States. Unfortunately, data suggests that long-term opioid use often begins from a discharge prescription intended to treat acute surgical pain. Additionally, opioid consumption during hospitalization is associated with adverse outcomes, including respiratory arrest, delirium, bowel ileus, nausea, and prolonged length of stay.

In efforts to decrease opioid exposure after surgery, medical providers at Vanderbilt University Medical Center (VUMC) employ a multi-modal approach to pain control, which includes strategic combinations of non-narcotic pain medications and regional nerve blocks. This intentional practice, termed 'enhanced recovery pathway', has been extremely successful over the last few years, with internal data showing significant reductions in opioid consumption, improved surgical outcomes, and earlier discharges from the hospital. Our results are consistent with experiences from other enhanced recovery programs.

Evidence is clear that combinations of non-narcotic pain medications with different mechanisms of actions are synergistically effective. What is not known, however, is the individual contribution of each medication to the overall efficacy of the regimen. Thus, we aim to perform a series of randomized, controlled trials in which we systematically isolate each component of our bundled pathway.

We propose to conduct a randomized controlled trial to investigate the weight of ketamine, within a the construct of a pre-established enhanced recovery program, on a) length of stay, b) total inpatient opioid consumption, and c) surgical outcomes after major abdominal surgery. Eligible patients in our enhanced recovery program will be randomized to receive either ketamine or saline during the perioperative period, with

the remainder of the multimodal analgesic regimen consistent between the groups. Breakthrough pain will be addressed pragmatically, in accordance with suggested pathway guidelines and routine practice of our physicians.

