## 8. Study procedures:

Procedure/Activity	Frequency
Patient randomization	Randomization will occur in clusters of one week. All patients in the same week will receive the same therapy (ketamine or placebo), with the choice being determined by a pre-generated random sequence.
intraoperative ketamine bolus (0.5mg/kg) vs placebo followed by continuous infusion 5 mcg/kg/min	once
postoperative ketamine infusion (2.5 mcg/kg/min, up to 100kg max) vs placebo for 48 hours	once
electronic medical record chart review	for data capture and statistical review

Data will be abstracted from the EMR. Some data will be obtained through the Research Derivative. The Research Derivative is a database of clinical and related data derived from the Medical Center's clinical systems and restructured for research. Data is repurposed from VU's enterprise data warehouse, which includes data from StarPanel, VPIMS, and ORMIS (Operating Room Management Information System), EPIC, Medipac, and HEO among others. The medical record number and other person identifiers are preserved within the database. Data types include reimbursement codes, clinical notes and documentation, nursing records, medication data, laboratory data, encounter and visit data, among others. Output may include structured data points, such as ICD 9 codes or encounter dates, semi-structured data such as laboratory tests and results, or unstructured data such as physician progress reports. The database is maintained by the Office of Research Informatics under the direction of [name].

**Due to a national shortage of ketamine, study enrollment was paused on April 3rd, 2023 and then resumed on September 18th, 2023.**

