## **12. Statistical considerations including sample size justification (power analysis) and statistical analysis plan (optional at this stage for investigators not versed in statistical methodology):**

This study is a cluster randomized, pragmatic clinical trial. Initial analysis will use descriptive statistics and data visualizations to both identify and address spurious values, and to characterize the study cohort. Characteristics will be grouped by study arm, but we do not plan to compare the study arms with statistical tests.

The primary outcome is length of stay, measured in days. It is expected that length of stay is a skewed distribution, and so non-parametric methods are preferred. However, it

is not possible to consider the clustering or baseline covariates using a Wilcoxon test. Therefore, a proportional odds regression model will be used. Clustering will be taken into account using a mixed-effects model. If there are patients included twice because they underwent two elective major abdominal surgeries, patient will also be included as a random effect. The model will include baseline characteristics such as age, BMI, history of substance use (smoking status and opioid status if available), and type of surgical procedure. The common odds ratio from the model will be estimated; this quantity can be interpreted similar to the concordance probability and is robust to the proportional odds assumption. We will also report the model-assisted estimands of mean and median length of stay. Bootstrapping will be used to generate appropriate confidence intervals.

We will use an intention to treat analysis and all participants who are randomized will be included in the statistical analysis and analyzed according to group assignment. Participants will be removed from the analysis if their provider deems the patient ineligible prior to study drug administration. If a participant or provider withdraws the participant from the study following study drug administration, the participant will receive care at the provider's discretion, but will remain in the statistical analysis.

The secondary outcomes will be explored in a similar way. The proportional odds model will be used to evaluate differences in opioid use in the hospital. Occurrence of events will be reported as rates with confidence intervals. Logistic regression will be used to compare the odds of events between groups.

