In all statistical modeling, emphasis will be placed on effect sizes over p-values. In addition, continuous variables will be modelled flexibly using cubic splines. Differential treatment effects will be explored by examining the interaction between the treatment indicator and the putative subgrouping variable. We will explicitly test for effects of treatment by sex. As before, continuous variables will not be categorized, and the interaction will be with the continuous variable. Subgroup analyses will not occur in reporting the main results of this trial unless there is evidence of a differential treatment effect.

To determine how long this trial will need to run to have sufficient power to detect a meaningful difference, we assumed 85% power, a type I error rate of 5%, and a 10% reduction in LOS. We estimated the within period correlation from preliminary data concerning the length of stay for major abdominal surgeries to be about 0.014. Given these assumptions, about 1514 patients would need to be included overall. If the effect size were bigger, say 20%, then 370 patients would be required. An increase in sample size is necessary to accommodate for the two post-randomization exclusions that are pre-specified. We expect ~30 participants to be impacted by these post-randomization exclusions and will therefore increase the sample size by 30 to account for this (n=1544). Given surgical volumes, we expect 20 patients to be enrolled each week, and for the trial to last approximately 18 months. The current accrual rate has been more aligned with ~15 patients enrolled each week. Accordingly, the trial is anticipated to last approximately 26 months.

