 - b. Mild side effects, but prefers discontinuation
 - c. Debilitating hallucinations
 - d. Debilitating dizziness
 - e. Hemodynamic instability
 - f. Other severe side effect

4. The incidence of ileus requiring gastric decompression as defined by orogastric or nasogastric tube placement in the postoperative period

Exploratory Outcomes

1. Instances of reoperation within the index encounter
2. VUMC hospital readmissions within 30 days post-discharge (not including ED visits)

Design Considerations

Randomization

Randomization will occur in clusters of one week. All patients in the same week will receive the same therapy (ketamine or placebo), with the selection being determined by a pre-generated random sequence.

Power and Sample Size

We anticipate the use of ketamine will reduce LOS following surgery start. To determine how long this trial will need to run to have sufficient power to detect a meaningful difference, we assumed 85% power, a type I error rate of 5%, and a 10% reduction in LOS. We estimated the within period correlation from preliminary data concerning the length of stay for major abdominal surgeries to be about 0.014. Given these assumptions, about 1514 patients would need to be included overall. An increase in sample size is necessary to accommodate for the two post-randomization exclusions that are pre-specified. We expect approximately 30 participants to be impacted by these post-randomization exclusions and will therefore increase the sample size by 30 to account for this exclusion (n=1544). Given surgical volumes, we expect 20 patients to be enrolled each week, and for the trial to last approximately 18 months.

Statistical Approach

Descriptive Analysis

We will describe the study cohort both overall and by treatment arm. To characterize the study sample, demographic and clinical data will be described. Categorical variables will be described using frequencies and proportions; continuous variables will be described using means and standard deviations as well as medians and interquartile ranges (IQR). Missingness will be recorded for each variable. To further assess the distribution of variables, graphical summaries will be displayed using graphs such as boxplots, dotplots, and/or histograms. No statistical testing will be performed to compare characteristics between groups. At a minimum, the following baseline variables will be described:

- Age (years)
- Sex assigned at birth (male, female, unknown)
- Race
 - Caucasian

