 - African American
 - American Indian
 - Asian
 - Decline to answer
 - White

- Hispanic/Latino/a
 - None of these
 - Other
 - Unknown
- Ethnicity (Hispanic/Latino, Non-Hispanic/Not Latino, Unknown)
- Weight (kg) and height (m²), and BMI (kg/m²) will be calculated with weight and height
- Van Walraven modified Elixhauser score
- History of Smoking
- Type of Surgical Procedure (colorectal, ventral hernia, or surgical oncology – mutually exclusive categories)
- Epidural vs. truncal nerve block
- Intraoperative time, as defined by anesthesia start time to anesthesia stop time
- The last American Society of Anesthesiologists (ASA) Physical Status classification associated with the surgery (anesthesia encounter)
- Opioid exposed or naïve, as defined by the perioperative medicine initial consult note
- Known history of anxiety, as defined as any code present in the patient's chart prior to, and including the date of enrollment
- Known history of depression, as defined as any code present in the patient's chart prior to, and including the date of enrollment
- Known history of PTSD, as defined as any code present in the patient's chart prior to, and including the date of enrollment

Main Analysis

The main statistical analyses will be performed with the intent-to-treat cohort. As a part of sensitivity analyses, the per-protocol analysis will be performed with the primary outcome and the first secondary outcome defined in Secondary Outcomes section (i.e., total consumption of post-enrollment inpatient opioids in morphine milligram equivalents).

Primary analysis: A mixed-effect proportional odds model will be used to compare the primary outcome (i.e., LOS) between the intervention and placebo arms with cluster as a random effect. The model will include baseline characteristics such as age, body mass index (BMI), Van Walraven modified Elixhauser score, history of smoking, epidural vs. truncal nerve block, intraoperative time, the last ASA Physical Status classification associated with the surgery, opioid naïve status, known history of anxiety, known history of depression, and known history of PTSD. Continuous variables will be modeled using cubic splines to examine non-linear relationship. For missing covariates, if the proportion of missingness is very small, single imputation will be used as appropriate; otherwise, multiple imputation will be used.

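### Weeks are randomised over about 26 months with a 24-week pause, but no calendar-time term is pre-specified; the analysis is valid without one, and adding one is a cheap precision gain of assumed size

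*SAP*

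**What the plan says.** **Allocation.** The SAP (Design Considerations, Randomization) states "Randomization will occur in clusters of one week", "with the selection being determined by a pre-generated random sequence". Neither document says whether the sequence was blocked or stratified by period.

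**Duration.** Protocol section 12, revised for an accrual of about 15 a week, says "the trial is anticipated to last approximately 26 months". The SAP still gives 20 a week and 18 months. Protocol section 8 adds "Due to a national shortage of ketamine, study enrollment was paused on April 3", with enrolment resuming on 18 September 2023. SAP version 1.0 is dated 6 September 2023, during that pause, and does not mention it.

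**Model.** The primary model is a proportional odds model comparing LOS "between the intervention and placebo arms with cluster as a random effect". On covariates the SAP says "The model will include baseline characteristics such as age, body mass index (BMI), Van Walraven modified Elixhauser score" and goes on to name eleven in all, each a characteristic of the patient or the procedure. Protocol section 12 has a shorter list: "The model will include baseline characteristics such as age, BMI, history of substance use", plus type of procedure. Neither list contains calendar time, season or the pause. The SAP's secondary analyses use the same covariates as the primary one.

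**The concern.** The week is the randomised unit, so calendar time varies at exactly the level at which treatment varies. A random week intercept treats the weeks as exchangeable. If LOS falls steadily, or steps at the restart, the model counts that movement as independent week-to-week noise and does not remove it. The treatment estimate is then less precise than it could be.

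The date of surgery is known for every patient and cannot be affected by the study drug, so nothing prevents adjustment for it. If the term is not written down in advance, adding it once the data have been seen would be a post hoc choice in the primary model. At stake is some power, and the chance to use a free baseline variable. The validity of the comparison is not at stake.

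**Working it through.** **Inputs from the documents.** 85% power; 5% type I error (two-sided assumed); 10% reduction in LOS; within-week correlation 0.014; N = 1514, or 1544 with 30 added for exclusions; 370 patients for a 20% reduction; 20 a week planned, about 15 observed.

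**Dates and span.** 3 April to 18 September 2023 is 168 days, or 24.0 weeks. 1544/15 = 103 enrolling weeks, or 23.7 months; with the pause, 29.2 months. The protocol's 26 months lies between the two. 1544/20 = 77 weeks, or 17.8 months, which is the SAP's 18.

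**The plan's own figure.** The SD of LOS is not given, so 1514 cannot be reproduced independently; it can only be solved backwards.
- Design effect at 20 a week: 1 + 19 × 0.014 = 1.266.
- N = 4(1.960 + 1.036)² × 1.266/d² = 1514 gives a standardised effect d = 0.1733.
- On the log scale, SD = |ln 0.9|/0.1733 = 0.608. On the raw scale, CV = 0.10/0.1733 = 0.577.
- Check at a 20% effect: the raw scale gives 378.5 and the log scale 338, against the stated 370. The SD is therefore approximate.

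**Baseline at 15 a week.** Design effect 1 + 14 × 0.014 = 1.196. Power = Φ(0.1733 × √(1514/(4 × 1.196)) − 1.960) = 86.9%.

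**Effect of a linear drift D over the trial (D is assumed).** Its share of total variance is v = (ln(1 − D))²/12 ÷ 0.608². If the drift is already inside 0.014, adjusting for it lowers the design effect to 1 + 14(0.014 − v). If it comes on top, the unadjusted design effect is 1 + 14(0.014 + v), and adjusting returns power to 86.9%.

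| Drift | v | Share of 0.014 | Design effect, inside and adjusted | Variance cut | Power, inside and adjusted | Power, on top and unadjusted |
|---|---|---|---|---|---|---|
| 5% | 0.0006 | 4% | 1.188 | 0.7% | 87.2% | 86.7% |
| 10% | 0.0025 | 18% | 1.161 | 2.9% | 87.9% | 86.0% |
| 15% | 0.0060 | 43% | 1.113 | 7.0% | 89.2% | 84.6% |
| 20% | 0.0112 | 80% | 1.039 | 13.1% | 91.1% | 82.6% |

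With the raw-scale CV (v = D²/12 ÷ 0.577²), the 20% drift case gives 90.7% instead of 91.1%, so the choice of scale matters little here.

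**Chance imbalance is the same quantity.** With 103 weeks, the SD of the error from early and late weeks falling unevenly between arms is |ln(1 − D)|/√12 × 2/√103. This is 0.6% of LOS at 10% drift and 1.3% at 20%. The standard error of the treatment effect is 2 × 0.608 × √(1.196/1514) = 0.034. The squared ratio is 3.1% at 10% drift and 13.8% at 20%, which matches the variance cuts of 2.9% and 13.1%. The imbalance is already inside the interval.

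**Simulation.** Weekly means, log SD 0.608, drift on top of 0.014, 3000 runs per cell, simple randomisation of weeks. Power without → with a linear time term:

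| Scenario | 20 a week | 15 a week |
|---|---|---|
| No drift | 0.84 → 0.83 | 0.86 → 0.86 |
| 10% drift | 0.81 → 0.82 | 0.85 → 0.86 |
| 20% drift | 0.76 → 0.83 | 0.81 → 0.86 |
| 10% drift plus 10% step at the pause | 0.73 → 0.82 | 0.80 → 0.86 |

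Without the term, type I error was 4.7% to 5.6% and the estimate was unbiased on average. If weeks were allocated in blocks of four (an assumption), the unadjusted test became conservative: 2.4% to 3.7% under 20% drift or drift plus step.

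**The case against.** The strongest reply is that nothing here is an error. Weeks are randomised, so time is independent of arm in expectation, and the week effect carries any drift into the standard error. That stands: the point concerns precision only.

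A reader might infer from protocol section 3 that LOS is known to be falling, since it cites "internal data showing significant reductions in opioid consumption, improved surgical outcomes, and earlier discharges from the hospital". That passage credits the adoption of the enhanced recovery pathway; it does not report a continuing trend, and the trial runs inside a programme already established. The pause is attributed to a drug shortage, and nothing links it to a change in LOS. So every drift size above is assumed.

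A reader might also count wider intervals and early/late imbalance as two harms. The working shows they are one.

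The sponsor can add that the 0.014 came from preliminary data and may already contain some drift, in which case the sample size has paid for it. At 15 a week, power is 86.9% before any adjustment, above the planned 85%. Case-mix covariates would also absorb part of any drift. All of this is fair, and it limits the size of the gain.

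The reply that the covariate lists are open (both are introduced by the words such as) is weaker. It permits a time term but does not pre-specify one.

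**Conclusion.** The point holds as a cheap improvement. It is not a defect that threatens the trial's conclusion. Without a calendar-time term the analysis is unbiased, with type I error near 5% under simple randomisation of weeks and possibly below 5% if the sequence was blocked. The stronger reading, that drift biases the result or inflates false positives, is not supported.

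The gain depends on an unknown drift. Counted inside 0.014, it is 0.3 of a percentage point of power at 5% drift, one point at 10%, and about four points at 20%. The last case needs 80% of all between-week variance to be a single linear trend. If drift comes on top of 0.014, the simulated recovery is about 1 point at 10% drift, and 5 to 9 points at 20% drift or drift plus a step. With no drift there is no gain. These figures rest on a back-solved SD, a linear trend, and a normal approximation to what will be a proportional odds analysis.

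**What to change.** Before unblinding, add one sentence to the SAP's Main Analysis. The primary and secondary models would include weeks since first enrolment as a cubic spline with 3 to 4 knots, optionally with a before/after-pause indicator, as fixed effects, with week kept as a random effect. The SAP already plans cubic splines for continuous variables, so no new method is needed.

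The cost is about 3 to 4 degrees of freedom among about 103 weeks. In the simulation with no drift, a linear term cost no more than about one point of power.

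In the same edit, state whether the weekly sequence was blocked, because that decides whether the unadjusted test could be conservative. Also reconcile the SAP's 18 months and 20 a week with the protocol's 26 months and 15 a week.

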Adult patients presenting on a weekday for an elective major inpatient abdominal surgery at VUMC will be screened for eligibility. Indications for exclusion will be noted if they meet criteria specified in the study protocol. Two post-randomization exclusions have been prespecified for this study. First, a patient directly transferred from the operating room to the Intensive Care Unit (ICU) with an endotracheal tube placed will not be included. The rationale is that these patients are exposed to both a sedative and narcotic infusion for the duration of their intubation, which would confound the ability to determine analgesic efficacy and/or side effects from the study drug. Furthermore, Enhanced Recovery After Surgery (ERAS) protocols are not followed in the ICU, and therefore there would be significant deviations from study protocol. Importantly, we aim to study ketamine's effects within ERAS principles for specifically elective surgeries. A transfer to the ICU while intubated reflects the occurrence of a major, unintended, and unanticipated intraoperative event for these elective procedures. The focus for that patient is no longer expedited recovery, but rather life-sustaining measures. Second, abortion of planned surgical procedure will qualify as a post-randomization exclusion. These patients do not undergo the intended surgical experience, will have different care pathways and goals, and are often discharged prior to 48 hours (length of time for the intervention). This exclusion will be defined as the patient being discharged home within 23 hours of anesthesia stop time, consistent with an 'observation' status rather than 'inpatient admission' to the hospital. Manual chart review will be performed to ensure appropriate exclusion. The occurrence of these exclusions will be tracked between study arms. Eligible patients will be consented for inclusion in the trial usually on the day of their surgery; patients returning for a follow up procedure that meets inclusion criteria will be reapproached for consent and rerandomized as appropriate.

Cohort Definition for Data Analysis

Intent-to-Treat Cohort

Intent-to-treat cohort includes all participants who are eligible and did not meet exclusion criteria specified in the study protocol.

Per-Protocol Cohort

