Secondary analyses: The secondary outcomes will be analyzed with the same covariates. A mixed-effect proportional odds model will be used to evaluate difference in opioid use in the hospital between the intervention and placebo arms. For each of the binary outcomes, a mixed-effect logistic regression will be used to compare the odds of events between the two arms.

Exploratory analyses: The exploratory outcomes will be presented in tables comparing the incidences of reoperation and hospital readmission within 30 days post-discharge between two arms.

Differential Treatment Effects

Differential treatment effects will be explored by examining the interaction between the treatment indicator and each variable that potentially interacts with treatment, one variable at a time, but subgroup analysis will not be performed. The variables we consider include sex, opioid naïve status, type of surgical procedure (colorectal, ventral hernia, or surgical oncology), epidural vs. truncal nerve block, known history of depression, and known history of PTSD.

References

5. Mercadante S. Opioid Analgesics Adverse Effects: The Other Side Of The Coin. *Curr Pharm Des.* 2019;25:1-6. doi:10.2174/1381612825666190717152226.

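### The SAP's named covariates for the primary and secondary models omit type of surgical procedure, which the protocol names and the SAP collects

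*SAP*

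**What the plan says.** Protocol section 12 specifies a mixed-effects proportional odds model for length of stay. Its named covariates are age, BMI, "history of substance use (smoking status and opioid status if available), and type of surgical procedure". It adds that, if a patient is included twice, "patient will also be included as a random effect".

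The SAP (Main Analysis, Primary analysis) specifies the same class of model, comparing length of stay "between the intervention and placebo arms with cluster as a random effect". Its covariate sentence begins "The model will include baseline characteristics such as age, body mass index (BMI), Van Walraven modified Elixhauser score, history of smoking" and goes on to block type, intraoperative time, ASA class, opioid naïve status, and history of anxiety, depression and PTSD. For the other outcomes: "The secondary outcomes will be analyzed with the same covariates".

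Procedure type appears elsewhere in the SAP. The baseline variables include "Type of Surgical Procedure (colorectal, ventral hernia, or surgical oncology", recorded as mutually exclusive categories. The Differential Treatment Effects section tests treatment interactions with six variables. Four of them are "type of surgical procedure (colorectal, ventral hernia, or surgical oncology), epidural vs. truncal nerve block, known history of depression, and known history of PTSD"; the other two are opioid status and sex.

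**The concern.** The SAP lengthens the protocol's covariate list but loses the variable that identifies the three enrolling surgical services. Nothing explains the loss, and the variable is defined and used in other parts of the same document, so it looks like an oversight.

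Two things are at stake. The first is pre-specification. In a proportional odds model, adding a prognostic covariate changes the conditional odds ratio being estimated even when the arms are perfectly balanced. Two different open lists therefore leave the primary odds ratio partly undetermined. The second is precision. Procedure type is known before treatment and already collected, so leaving it out may give up power at no saving. Treatment is assigned by week, and chance differences in service mix between arms would be adjusted only indirectly, through whatever the other covariates carry.

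**Working it through.** **1. Compare the lists.**

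| Variable | Protocol model | SAP model | SAP interaction test |
|---|---|---|---|
| Age | yes | yes | no |
| BMI | yes | yes | no |
| Smoking | yes | yes | no |
| Opioid status | yes (if available) | yes | yes |
| **Type of surgical procedure** | **yes** | **no** | **yes** |
| Elixhauser score, intraoperative time, ASA class, anxiety | no | yes | no |
| Block type, depression, PTSD | no | yes | yes |
| Sex | no | no | yes |

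The protocol list minus the SAP list leaves procedure type alone. If smoking and opioid status are counted as one item (substance use), the protocol names four covariates and procedure type is still the only one dropped. Of the six interaction variables, four are in the SAP's covariate list. The other two are procedure type and sex, and sex was never on the protocol's covariate list.

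**2. Power by formula.** Inputs from the SAP (Power and Sample Size) are 85% power and 5% type I error, taken here as two-sided. I treat 85% as the power of the SAP's listed model; the documents do not say whether the calculation was covariate-adjusted. Let R² be the share of variation in stay that procedure type explains beyond the eleven listed covariates. No value is given, so R² is an assumed range.

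Power = Φ((1.960 + 1.036)/√(1 − R²) − 1.960)

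| R² | 2.996/√(1 − R²) | Power |
|---|---|---|
| 0% | 2.996 | 85.0% |
| 2% | 3.026 | 85.7% |
| 5% | 3.074 | 86.7% |
| 10% | 3.158 | 88.5% |
| 15% | 3.250 | 90.1% |

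**3. Power by simulation of the SAP's model class.** A proportional odds model with a week random intercept was fitted with and without procedure type to the same data, using 2,475 datasets per R².

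- Taken or derived from the documents: 15 patients per week, week correlation 0.014 (applied on the latent scale), and 101 weeks × 15 = 1,515 encounters, close to the planned 1514. The weeks were split 51 and 50 between arms.
- Assumed: ten equal length-of-stay categories; one score for the listed covariates explaining 20% of latent variance; service shares of 40/25/35%; procedure type explaining R² of the remaining variance; true conditional odds ratios of 0.746, 0.741, 0.735 and 0.728 at the four R² values, set to give roughly 85% power without procedure type.

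| R² | OR without → with | SE without → with | Power without → with | Change in points (Monte Carlo SE) | Ratio of mean z |
|---|---|---|---|---|---|
| 0% | 0.746 → 0.746 | 0.099 → 0.099 | 83.9% → 83.6% | −0.3 (0.2) | 1.000 |
| 5% | 0.748 → 0.740 | 0.099 → 0.100 | 81.6% → 84.1% | +2.5 (0.5) | 1.028 |
| 10% | 0.751 → 0.736 | 0.098 → 0.099 | 83.2% → 86.6% | +3.4 (0.5) | 1.058 |
| 15% | 0.750 → 0.727 | 0.098 → 0.100 | 83.0% → 88.7% | +5.8 (0.6) | 1.091 |

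The simulated powers without procedure type fall somewhat below 85%, so the z ratios are a cleaner basis for comparison. Φ(2.996 × ratio − 1.960) gives 85.0%, 86.9%, 88.7% and 90.5%, close to the formula.

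The standard error hardly moves. The gain comes from the odds ratio moving away from 1, which is the change of estimand described above.

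**4. Random effects.** The SAP's Study Population section says that "patients returning for a follow up procedure that meets inclusion criteria will be reapproached for consent and rerandomized as appropriate", so one patient can contribute two encounters. The SAP names only cluster as a random effect; the protocol adds patient in that case. No repeat rate is given, and no material effect on type I error is claimed.

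**The case against.** The best reply is that the documents do not firmly conflict. Both covariate lists are introduced by 'such as', so the SAP does not exclude procedure type. The protocol text that names it records the restart of enrollment on 18 September 2023, after the SAP date of 6 September 2023. Read together, the documents allow the variable in the model. That is correct, but leaving the choice open until the data are in is the freedom a SAP is meant to remove, and the named list taken as written omits the variable.

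Second, block type, intraoperative time, ASA class and Elixhauser score may already carry much of the same information. This also stands as a caution. R² is defined as variation beyond those covariates, and the range includes 0%.

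Third, the size is assumed throughout. The formula also lets procedure type reduce the between-week variance, which it need not do. Keeping that part fixed at 15 per week, the variance ratio is (0.21 + 0.986(1 − R²))/1.196, and power is 86.4%, 87.9% and 89.3% at 5%, 10% and 15%. This lowers the gain by less than one point. The documents cannot show that any power is actually lost.

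Finally, the patient random effect is conditional in the protocol and simply not mentioned in the SAP. It adds no weight to the main point.

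**Conclusion.** The point holds. Type of surgical procedure is the only protocol covariate missing from the SAP's named list; the gap extends to the secondary models and is unexplained. The omission itself is certain from the text. The benefit of correcting it is not: relative to 85%, the gain is 0, about 2, about 3 to 4, or about 4 to 5.5 points if procedure type explains a further 0%, 5%, 10% or 15% of the variation, across the formula, the rescaled simulation and the fixed-week-variance variant. These figures rest on assumed variance shares and on 85% being the power of the listed model.

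No bias and no inflation of type I error is claimed. The case for changing the plan is a primary odds ratio fixed in advance and a possible gain in power at almost no cost. It should be corrected, but it does not threaten the trial's validity.

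**What to change.** Before unblinding, amend the SAP's Main Analysis as follows:

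- Add type of surgical procedure (colorectal, ventral hernia, surgical oncology) to the primary and secondary models. If it was left out on purpose, state the reason.
- Remove 'such as' and give one final covariate list, matched to the protocol or with the differences explained.
- In the same edit, state whether patient is a random effect when a patient contributes more than one encounter, as the protocol provides.

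The cost is wording and two degrees of freedom. The variable is already collected in the form needed.
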